7.2.1.6. Time to Progression (TTP)

TTP is defined as the time from randomization until the earliest date of confirmed PD per IMWG, or death due to PD.

TTP will be analysed at the time of final ORR analysis, also at study close out if applicable, based on responses assessed by both IRC and investigator.

A summary of the assignments for progression and censoring dates for TTP are specified in Table 5.

Table 5 Assignments for Progression and Censoring Dates for TTP Analysis

Situation	Date of Event (Progression/Death) or Censoring	Outcome Event (progression/Death) Or Censored
No (or inadequate) baseline tumor assessments ^[1] and the subject has not died (if the subject has died follow the rules for death indicated at the bottom of the table)	Randomization	Censored
No post-baseline assessments and the subject has not died (if the subject has died follow the rules for death indicated at the bottom of the table)	Randomization	Censored

Situation	Date of Event (Progression/Death) or Censoring	Outcome Event (progression/Death) Or Censored
Progression documented at or between scheduled visits	Date of assessment of progression ^[1]	Event
No progression (or death)	Date of last 'adequate' assessment of response ^[2]	Censored
New anticancer treatment started (prior to documented disease progression or death) ^[3] .	Date of last 'adequate' assessment of response ^[2] (on or prior to starting anti-cancer therapy)	Censored
Death due to progression without extended loss-to-follow-up time	Date of death	Event
Death from causes other than progression without extended loss-to-follow-up time	Date of death	Censored
Death or progression after an extended loss-to-follow-up time (two or more missed cycles + 7 day window) ^[4]	Date of last 'adequate' assessment of response ^[2] prior to PD/death (prior to missed assessments)	Censored
Death or progression after an extended loss-to-follow-up time from randomization	Date of randomization	Censored

Adequate baseline assessment is defined as at baseline, a patient has at least one of the following measurements: a. Serum M-protein ≥ 0.5 g/dL (≥ 5 g/L) or b. Urine M-protein ≥ 200 mg/24h or c. Serum FLC assay: Involved FLC level ≥ 5 mg/dL (≥ 50 mg/L) and an abnormal serum free light chain ratio (<0.26 or >1.65).

An adequate assessment is defined as an assessment where the IRC/Investigator determined response is sCR, CR, VGPR, PR, MR, or SD.

If PD or death and New anti-cancer therapy occur on the same day assume the progression or death was documented first (e.g., outcome is progression or death and the date is the date of the assessment of progression or death). If anti-cancer therapy is started prior to any adequate assessments, censoring date should be the date of randomization.

Refer to Section 15.5.4 "Extended Loss to Follow-up or Extended Time without an Adequate Assessment".

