1.1. RAP Amendments

Revision chronology:

RAP Section	Amendment Details
Reporting and Analysis Plan_Study205678_Final_V1 [02-MAY-2019]	
Reporting and Analysis Plan_Study205678_Amendment_Final_V1 [16-JUL-2019]	
Reporting and Analysis Plan_Study205678_Amendment2_Final_V1 [06 Apr 2022]	
RAP Authors/Team Approval	
 Update the approvers.
Section 2.1 Changes to the Protocol Defined Statistical Analysis Plan	
 Updated protocol version and document number
Section 2.3 Study design	
 Updated reference to IA section per PA06.
Section 3.1 Interim analyses	
 Updated protocol version and document number
Section 3.1.2 Additional Comparative Futility Stopping Rule Based on Bayesian Approach	
 Update protocol document number
Section 3.2 primary analysis	
 Updated reference to end of study section per PA06.
Section 6.2 disposition of subjects	
 Added analysis regarding visits and assessments Impacted by COVID-19 Pandemic will be presented
Section 6.5 Extent of exposure	
 Added listing of all dose delays due to corneal events (GSK scale) and listing of dose delays and associated Eye Disorder Events (CTCAE) Added analysis for duration of exposure by response category, Added KM curve for time to treatment discontinuation by response category and for subject who received at least 3 cycle of the study treatment Added Swim-lane plot for duration of study treatment for responder based on IRC
Section 7.2.1.5 Progression Free survival Table 4	
 Updated Adequate baseline assessment definition for Serum FLC assay: Involved FLC level ≥ 10 mg/dL (≥ 100 mg/L) based on PA06
Section 7.2.1.7 Overall survival	
 Updated reference to end of study section per PA06.
Section 7.2.2 Summary measure	
 Added a KM curve for Duration of response by dose delay category , by response category per IRC. Added Hazard ratio estimate by Pike estimator. Added a summary for time to best response based on IRC Added KM curve for PFS and Overall survival by response category per IRC.

RAP Section	Amendment Details
Reporting and Analysis Plan_Study205678_Final_V1 [02-MAY-2019]	
Reporting and Analysis Plan_Study205678_Amendment_Final_V1 [16-JUL-2019]	

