2. SUMMARY OF KEY PROTOCOL INFORMATION

2.1. Changes to the Protocol Defined Statistical Analysis Plan

There were no changes or deviations to the originally planned statistical analysis specified in the protocol amendment 6 GSK Document Number [TMF-13990464](#) (Dated: 19-Nov-2021).

[figure not shown]

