7.2.1.3. Duration of Response (DoR)

DoR is defined as the time from first documented evidence of confirmed PR or better until the earliest date of confirmed disease progression (PD) per IMWG, or death due to PD among participants who achieve a response (i.e., confirmed PR or better). Responders without confirmed PD will be censored at the censoring time point for Time to Progression as specified in [Table 5](#) of Section [7.2.1.6](#).

DoR will be analysed at the time of final ORR analysis, also at study close out if applicable, based on responses assessed by both IRC and investigator.

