7.2.1.5. Progression Free Survival (PFS)

PFS is defined as the time from randomization until the earliest date of confirmed PD per IMWG, or death due to any cause.

PFS will be analysed at the time of final ORR analysis, also at study close out if applicable, based on responses assessed by both IRC and investigator.

A summary of the assignments for progression and censoring dates for PFS are specified in [Table 4](#) below.

Table 4 Assignments for Progression and Censoring Dates for PFS Analysis

Situation	Date of Event (Progression/Death) or Censoring	Outcome Event (Progression/Death) Or Censored
No (or inadequate) baseline tumor assessments ^[1] and the subject has not died (if the subject has died follow the rules for death indicated at the bottom of the table)	Randomization	Censored
No post-baseline assessments and the subject has not died (if the subject has died follow the rules for death indicated at the bottom of the table)	Randomization	Censored
Progression documented without extended loss-to-follow-up time	Date of assessment of progression ^[1]	Event
No progression (or death)	Date of last 'adequate' assessment of response ^[2]	Censored
New anticancer treatment started (prior to documented disease progression or death) ^[3] .	Date of last 'adequate' assessment of response ^[2] (on or prior to starting anti-cancer therapy)	Censored
Death without extended loss-to-follow-up time	Date of death	Event
Death or progression after an extended loss-to-follow-up time (two or more missed cycles + 7 day window) ^[4]	Date of last 'adequate' assessment of response ^[2] prior to PD/death (prior to missed assessments)	Censored

Situation	Date of Event (Progression/Death) or Censoring	Outcome Event (Progression/Death) Or Censored
Death or progression after an extended loss-to-follow-up time from randomization	Date of randomization	Censored

[1] Adequate baseline assessment is defined as at baseline, a patient has at least one of the following measurements:
a. Serum M-protein ≥ 0.5 g/dL (≥ 5 g/L) or b. Urine M-protein ≥ 200 mg/24h or c. Serum FLC assay: Involved FLC level ≥ 10 mg/dL (≥ 100 mg/L) and an abnormal serum free light chain ratio (<0.26 or >1.65)

[2] An adequate assessment is defined as an assessment where the IRC/Investigator determined response is sCR, CR, VGPR, PR, MR, or SD.

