responses. Summary of Time to Best Response based on Independent Reviewer - Assessed Response will also be provided.

- PFS will be summarized using Kaplan-Meier method by dose level. If there is a sufficient number of progressions or deaths, median PFS, first and third quartiles, 6-month PFS rate, and 95% CIs will be estimated using the Brookmeyer-Crowley method [Brookmeyer, 1982]. A figure and listing of PFS time will also be provided. Analysis of PFS will be based on both IRC and investigator-assessed responses. Summary and Kaplan Meier curve by Response Category Based on Independent Reviewer-Assessed Response will be provided.
- TTP will be summarized using Kaplan-Meier method by dose level. If there is a sufficient number of progressions or death due to PD, median TTP, first and third quartiles and 95% CI, will be estimated using the Brookmeyer-Crowley method [Brookmeyer, 1982]. A figure and listing of TTP time will also be provided. Analysis of TTP will be based on both IRC and investigator-assessed responses.
- OS will be summarized using the Kaplan-Meier method by dose level. For each dose level, the Kaplan-Meier estimates for the median overall survival time, the first and third quartiles will be presented, along with 95% CIs if there are a sufficient number of deaths. A graph of survival curves and a listing of survival times will also be provided. In addition, pending on maturity of data, the survival probability at 6, 12 and 18 months with 95% CI will be estimated using Kaplan-Meier method. Summary and Kaplan Meier curve by Response Category Based on Independent Reviewer-Assessed Response will be provided.

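### PFS and TTP set different involved-FLC thresholds for an adequate baseline (10 vs 5 mg/dL), so one confirmed progression can be a TTP event yet be censored at randomization for PFS

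*SAP*

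**What the plan says.** Section 7.2.1.5, Table 4, governs event and censoring dates for PFS. Its footnote on adequate baseline asks for at least one of three measurements, the third being "Serum FLC assay: Involved FLC level ≥ 10 mg/dL" (100 mg/L) with an abnormal FLC ratio.

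Section 7.2.1.6, Table 5, does the same for TTP. The serum M-protein, urine M-protein and FLC-ratio criteria are identical, but the FLC level is "Serum FLC assay: Involved FLC level ≥ 5 mg/dL" (50 mg/L).

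The first row of each table censors at randomization a participant with no or inadequate baseline who is alive. Its only exception is death: "if the subject has died follow the rules for death indicated at the bottom of the table". A later row in each table makes documented progression an event on its assessment date.

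Three other places bear on the point:

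- Section 1.1 logs, for Section 7.2.1.5 Table 4, "Updated Adequate baseline assessment definition for Serum FLC assay", giving the 10 mg/dL value and naming protocol amendment 6 as its basis. There is no matching entry for Table 5.
- Section 2.1 states "There were no changes or deviations to the originally planned statistical analysis specified in the protocol amendment 6".
- Section 7.2.1.3 borrows Table 5 for DoR: "Responders without confirmed PD will be censored at the censoring time point for Time to Progression".

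**The concern.** TTP counts confirmed PD or death due to PD. PFS counts confirmed PD or death from any cause. Every TTP event should therefore also be a PFS event on the same date. Two thresholds for one baseline concept break this for participants who qualify by FLC alone and lie between the two values.

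Both values are current text, so this is not a difference between the amendment log and the plan. The log only suggests how it arose: a conforming edit reached one table and not the other. Section 2.1 declares no departure from amendment 6, and nothing presents the difference as intended.

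At stake are the descriptive PFS and TTP summaries. IRC-assessed PFS and TTP (Tables 2.0080 and 2.0100) are both scheduled for the primary and the end-of-study deliverables, so the mismatch carries into the end-of-study output. DoR becomes involved only through the Table 5 censoring dates it adopts. ORR, the only tested endpoint, is not affected.

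**Working it through.** **1. The rules applied to one type of participant.** Take a living participant with serum and urine M-protein below their thresholds, confirmed PD, no new anti-cancer therapy before PD and no extended gap. Apply row 1 first, then the progression row.

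| Involved FLC (mg/dL) | Ratio | PFS (threshold 10) | TTP (threshold 5) |
|---|---|---|---|
| 4.9 | abnormal | censored at randomization | censored at randomization |
| 5, 7, 9.9 | abnormal | **censored at randomization** | **event at PD** |
| 10, 12 | abnormal | event at PD | event at PD |
| any of these | normal | censored at randomization | censored at randomization |

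The endpoints disagree only from 5 to below 10 mg/dL. The units are consistent in each footnote (10 mg/dL = 100 mg/L; 5 mg/dL = 50 mg/L), so this is not a unit slip.

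*Example.* FLC 7 mg/dL, abnormal ratio, last adequate assessment day 64, confirmed PD day 85. The gap is 85 − 64 = 21 days, inside the 49-day window of Section 15.5.4. TTP: event on day 85. PFS: censored at randomization.

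**2. Size, if Table 5 is aligned to 10 mg/dL.** The SAP does not give the number in the band. Assume 100 participants, S progression-free at month 6, no other censoring, and k band participants who progress before month 6. Alignment turns those k from TTP events into time-0 censorings, so the Kaplan-Meier proportion at month 6 goes from S/100 to S/(100 − k).

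| S | k = 0 | k = 1 | k = 5 |
|---|---|---|---|
| 30 | 30.0% | 30/99 = 30.3% | 30/95 = 31.6% |
| 40 | 40.0% | 40/99 = 40.4% | 40/95 = 42.1% |
| 50 | 50.0% | 50/99 = 50.5% | 50/95 = 52.6% |

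PFS does not change, because these participants are already censored at day 0 there. The value k = 5 is an illustrative upper figure with no source.

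**3. The planned TTP summary.** Section 7.2.2 says "median TTP, first and third quartiles and 95% CI, will be estimated using the Brookmeyer-Crowley method". Assume exponential times with rate λ = −ln(S/100)/6 and F0(t) = 1 − exp(−λt), the k progressors being spread over months 0 to 6 in proportion to all events. When the median falls before month 6 it solves

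F0(t) = 0.5(100 − k) / (100 − k/F0(6)).

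For S = 40: λ = 0.9163/6 = 0.1527 per month and F0(6) = 0.6.

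- k = 0: F0 = 0.5, t = 0.6931/0.1527 = 4.54 months.
- k = 1: F0 = 49.5/98.33 = 0.5034, t = 4.58 months.
- k = 5: F0 = 47.5/91.67 = 0.5182, t = 4.78 months.

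For S = 30 the medians are 3.45, 3.48 and 3.57 months. For S = 50 the median falls at or after month 6, so it solves F0(t) = [0.5(100 − k) + k]/100, giving 6.00, 6.09 and 6.44 months.

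**4. Size, if Table 4 is aligned to 5 mg/dL instead.** TTP does not change and PFS moves the other way, from S/(100 − k) to S/100; for S = 40 and k = 5, from 42.1% to 40.0%.

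**The case against.** The strongest objection is that Tables 4 and 5 state no order of precedence. A living progressor with an inadequate baseline fits both row 1 and the progression row; the instruction to take the first applicable line belongs to Table 3. If the progression row prevailed, PD would be an event for both endpoints and the headline example would disappear. This stands as an ambiguity. Row 1 prevailing is still the plain reading, because death is its only exception. The adequate-baseline marker on the progression date is weak support and may be a leftover. Under the other reading the footnotes still conflict: a living participant in the band without PD, but with adequate later assessments, is censored at randomization for PFS and at the last adequate assessment for TTP.

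Second, the affected group may be empty: FLC-only, within a narrow band, abnormal ratio, progressed, alive. Deaths remove participants from it by end of study. Even k = 5 moves the median by 4.78 − 4.54 = 0.24 months, about a week, against a three-week assessment interval. The endpoints are descriptive and the rule is the same in both arms. All of this is conceded and limits the importance of the point.

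Third, DoR uses Table 5 alone, so the mismatch creates no inconsistency within DoR today. That is right; DoR matters because of one direction of the fix. It is also true that row 1 can already send a living responder below 5 mg/dL to censoring before response onset. That is a separate existing gap.

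Fourth, amendment 6 is not at hand, so Section 2.1 cannot show which footnote departs from it. Hence the value has to be confirmed there.

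**Conclusion.** The concern holds. Two current footnotes define the same baseline concept differently, without a stated reason. Followed as written, they let one confirmed PD count for TTP and be censored at randomization for PFS. The contradiction is certain; the event-versus-censored outcome also rests on row 1 taking precedence over the progression row.

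The size is probably small and may be zero. Under the stated assumptions with S = 40, the 6-month TTP proportion changes by 0.4 percentage points for k = 1 and 2.1 for k = 5. Only descriptive secondary endpoints are concerned, and no claim is made about participants who died. It should be corrected before the end-of-study analysis because the correction is cheap and the present text is incoherent.

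**What to change.** 1. Use one adequate-baseline definition in both footnotes, confirmed against protocol amendment 6. The log points to the Table 4 value.
2. Log the change for whichever table is altered.
3. Re-derive the affected endpoint at end of study (TTP if Table 5 changes, PFS if Table 4 changes) and report any difference in definition from the primary analysis. Section 12.2 describes work at the primary analysis in the past tense and this amendment is dated 06 Apr 2022, so that analysis is already done.
4. If Table 5 is raised to 10 mg/dL, state in Section 7.2.1.3 that its inadequate-baseline row does not apply to DoR. Otherwise living responders at 5 to below 10 mg/dL without confirmed PD would be censored at randomization, before their response began. All other Table 5 censoring rows should stay in force for DoR, including the date of death for "Death from causes other than progression without extended loss-to-follow-up time" and the limit set by new anti-cancer therapy.
5. As an optional clarification, state in both tables that row 1 takes precedence over the progression row.

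The cost is one footnote value, one log entry, one DoR sentence if Table 5 is the table changed, a re-run of one endpoint at end of study, and a note in the report.

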7.2.1.7. Overall Survival (OS)

OS is defined as the time from randomization until death due to any cause. Participants who withdraw consent from the study or are lost to follow-up will be censored at the time of withdrawal or lost to follow-up. Participants who do not have a death record at the clinical cut-off date for the analysis will be censored at the last known alive date. The last contact date will be determined by the maximum collection/assessment date from among selected data domains within the clinical database.

An OS analysis will be performed at the time of the primary ORR analysis. An updated OS analysis will be performed at the end of study as defined in Section 4.6 of the protocol.

7.2.2. Summary Measure

- For ORR based on investigator-assessed responses, the number and percentage of participants with BOR in the following response categories will be summarized by dose level: sCR, CR, VGPR, PR, overall response (sCR+CR+VGPR+PR), minimal response (MR), stable disease (SD), progressive disease (PD), and not evaluable (NE). The corresponding 2-sided 97.5% exact CI for ORR will also be provided. Participants with unknown or missing responses will be treated as non-responders, i.e., these participants will be included in the denominator when calculating percentages of response. A list of investigator-assessed response at each visit will be listed. In addition, a summary table of IRC-assessed and investigator-assessed best response with confirmation will be provided to assess the concordance rate.
- For CBR, the number and percentage of participants with the BOR in the following response categories will be summarized by dose level: sCR, CR, VGPR, PR, MR, clinical benefit response (sCR+CR+VGPR+PR+MR), SD, PD, and NE. The corresponding exact 95% CI for CBR will also be provided. Participants with unknown or missing responses will be treated as non-responders, i.e., these participants will be included in the denominator when calculating percentages of response. Analysis of CBR will be based on both IRC and investigator assessed responses assessed by both IRC and investigator.
- DoR will be summarized using Kaplan-Meier method by dose level for participants with a confirmed PR or better. If there are a sufficient number of responders who subsequently progress or die due to PD, median DoR, first and third quartiles and 95% CI, will be estimated using the Brookmeyer-Crowley method [Brookmeyer, 1982]. A figure and listing of DoR time will also be provided. Analysis of DoR will be based on both IRC and investigator-assessed responses. A Kaplan Meier curve of Duration of Response by Dose Delay Category Based on Independent Reviewer - Assessed Response will be provided. A Kaplan Meier curve of Duration of Response by Response Category based on Independent Reviewer-Assessed Response will be provided. Hazard ratio estimated using the Pike estimator will be provided.
- TTR will be summarized descriptively if there are sufficient number of responses by dose level, using median(s) and quartiles for participants with a confirmed response of PR or better. Analysis of TTR will be based on both IRC and investigator-assessed

responses. Summary of Time to Best Response based on Independent Reviewer - Assessed Response will also be provided.

- PFS will be summarized using Kaplan-Meier method by dose level. If there is a sufficient number of progressions or deaths, median PFS, first and third quartiles, 6-month PFS rate, and 95% CIs will be estimated using the Brookmeyer-Crowley method [Brookmeyer, 1982]. A figure and listing of PFS time will also be provided. Analysis of PFS will be based on both IRC and investigator-assessed responses. Summary and Kaplan Meier curve by Response Category Based on Independent Reviewer-Assessed Response will be provided.
- TTP will be summarized using Kaplan-Meier method by dose level. If there is a sufficient number of progressions or death due to PD, median TTP, first and third quartiles and 95% CI, will be estimated using the Brookmeyer-Crowley method [Brookmeyer, 1982]. A figure and listing of TTP time will also be provided. Analysis of TTP will be based on both IRC and investigator-assessed responses.
- OS will be summarized using the Kaplan-Meier method by dose level. For each dose level, the Kaplan-Meier estimates for the median overall survival time, the first and third quartiles will be presented, along with 95% CIs if there are a sufficient number of deaths. A graph of survival curves and a listing of survival times will also be provided. In addition, pending on maturity of data, the survival probability at 6, 12 and 18 months with 95% CI will be estimated using Kaplan-Meier method. Summary and Kaplan Meier curve by Response Category Based on Independent Reviewer-Assessed Response will be provided.

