7.1. Primary Efficacy Analyses

7.1.1. Overall Response Rate (ORR) based on IRC assessment

ORR, defined as the percentage of participants with a confirmed partial response (PR) or better (i.e., PR, very good partial response [VGPR], complete response [CR] and stringent complete response [sCR]), according to the 2016 International Myeloma Working Group (IMWG) Response Criteria [Kumar, 2016]. ORR based on Independent Review Committee (IRC) will be analyzed as the primary endpoint.

ORR at primary analysis will be analyzed based on the confirmed responses, which will be derived based on the algorithm specified in [Table 3](#).

Only the assessments from the start of treatment up to the earlier of confirmed disease progression or the start of new anti-cancer therapy will be considered. Only new systemic anti-cancer drugs taken are considered as anti-cancer therapy (radiotherapy and surgeries are not considered as systemic anti-cancer therapy for the purpose of this analysis).

Subjects with only assessments of Not Evaluable or missing response will be treated as non-responders; i.e. they will be included in the denominator when calculating the percentage.

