7.1.1.1. Derivation of Confirmed Response

The derivation of confirmed response shall be based on the algorithm specified in [Table 3](#). The date of the first of the two consecutive assessments will be used as the date of the confirmed response.

Table 3 Response confirmation algorithm

#	Response at the First Time Point	Response at Subsequent Disease Assessment ¹	Confirmed Response at the First Time Point
1	sCR	sCR	sCR
2	sCR	CR	CR
3	CR	sCR/CR	
4	sCR/CR	VGPR	VGPR
5	VGPR	sCR/CR/VGPR	
6	sCR/CR/VGPR	PR	PR
7	PR	sCR/CR/VGPR/PR	
8	sCR/CR/VGPR/PR	MR	MR
9	MR	sCR/CR/VGPR/PR/MR	

#	Response at the First Time Point	Response at Subsequent Disease Assessment ¹	Confirmed Response at the First Time Point
10	sCR/CR/VGPR/PR/MR	SD	SD
11	sCR/CR/VGPR/PR/MR	PD (any reason) OR No subsequent disease assessment: subject died or discontinued study or started new anti-cancer therapy before further adequate disease assessment	NE
12	PD (due to reasons other than imaging, i.e., plasmacytoma or bone lesion)	PD (any reason) including PD after initiation of new anti-cancer therapy OR No subsequent disease assessment: subject died due to PD before further adequate disease assessment (including death due to PD after initiation of new anti-cancer therapy)	PD
13	PD (due to reasons other than imaging, i.e., plasmacytoma or bone lesion)	sCR/CR/VGPR/PR/MR/SD OR No subsequent disease assessment: subject died due to reasons other than PD before further adequate disease assessment OR No subsequent disease assessment: subject discontinued study before further adequate disease assessment	NE
14	sCR/CR/VGPR/PR/MR/PD (due to reasons other than imaging, i.e., plasmacytoma or bone lesion)	No subsequent disease assessment: subject has not died, discontinued from study or (except for PD) started new anti-cancer therapy; but as yet has no further adequate disease assessments	Unconfirmed sCR/CR/VGPR/PR/MR/PD. Will be categorized as NE for final ORR analysis. For ORR analysis in IA, the UC response (PR or better) will be counted as responder.
15	SD	Any OR No subsequent disease	SD

#	Response at the First Time Point	Response at Subsequent Disease Assessment ¹	Confirmed Response at the First Time Point
		assessment	
16	PD due to imaging (plasmacytoma or bone lesion)	Any OR No subsequent disease assessment	PD
17	NE or missing	Any OR No subsequent disease assessment	NE

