1. Subsequent disease assessment is defined as the next adequate (not missing or NE) disease assessment following the first timepoint before (or on the same date of) start of new anti-cancer therapy except for confirmation of PD, for which PD or death due to PD after new anti-cancer therapy are considered for confirmation of PD. No minimal time interval is required for the subsequent disease assessment, but a different sample is required for confirmation.
2. SD does not need to be confirmed.
3. PD due to imaging (i.e., plasmacytoma or bone lesion) does not need to be confirmed.
4. Where criteria are not mutually exclusive, take the first that applies.

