7.2.4. Statistical Analyses / Methods

Details of the planned displays are provided in [Appendix 13](#): List of Data Displays and will be based on GSK data standards and statistical principles.

Unless otherwise specified, endpoints / variables defined in Section [7.2.1](#) will be summarised using descriptive statistics, graphically presented (where appropriate) and listed.

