8.2.3. Corneal events (GSK scale)

Following discussions with regulatory agencies, GSK developed a grading scale to capture both corneal examination findings and visual acuity changes in participants treated with GSK2857916. This GSK scale differs from the CTCAE criteria for eye disorders which relies mainly on patient's symptoms and patient's ability to attend to 'activities of daily living' for grading of events. Details of derivation this GSK scale based on corneal findings and visual acuity Ophthalmic Exam (collected from Ocular

form) can be found in Appendix 9 Table 22 and Table 23 of study protocol (Version: GSK Document Number [TMF-13990464](#)).

In addition to the listing, the following outputs will be provided for corneal events graded using the GSK scale:

1. Overview for corneal event (GSK scale)
2. Summary of grade of GSK scale
 - a. Summary of characteristics of corneal events (GSK scale) including the percentage of duration of exposure (see Section 15.6.2 for definition) with corneal events (GSK scale) of grade ≥ 2 and grade ≥ 3 respectively
 - b. Summary of onset time and duration of the first occurrence of corneal event (GSK scale) of a) grade 2 or above; 2) grade 3 or above.
3. Summary of actions taken with study treatment (e.g. dose reduction/delay/permanent discontinuation)
4. Summary of time to re-initiation of study treatment post treatment delay due to corneal events (GSK scale)
5. Change in grade of corneal events (GSK scale) from EOT to last follow-up
6. Summary of worst post-baseline corneal events (GSK scale)
7. Summary of worst post-baseline corneal events (GSK scale) by best response (PR or better vs. otherwise)
8. Summary of resolution (improve to grade 1 or better) in corneal events (GSK scale) during Follow-up period (from EOT visit to last follow-up visit).
9. Logistic regression analysis will be performed to explore possible risk factors for developing corneal Events (GSK scale ≥ 2). In addition to dose arm (3.4 mg/kg vs 2.5 mg/kg), Sex (Male vs Female), Age Group (< 65 vs. ≥ 65 years), Race (White, Other), the following risk factors will also be considered:
 - a. History of intraocular surgery: (Yes vs. No)
 - b. Lens status (pseudophakia vs natural lens) at baseline
 - c. Known history of dry eye per screening questionnaire (Presence vs. Absence)
 - d. Presence of keratopathy at baseline exam (None vs. Mild vs. Moderate/Severe)

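### PFS and OS by IRC response category are run from randomization with no landmark or time-dependent handling, so any split of confirmed responders from other patients favours responders

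*SAP*

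**What the plan says.** **Time origin.** SAP Section 7.2.1.5: "PFS is defined as the time from randomization until the earliest date of confirmed PD per IMWG, or death due to any cause". Section 7.2.1.7: "OS is defined as the time from randomization until death due to any cause".

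**The displays.** In Section 7.2.2 the PFS and OS bullets each end with the same commitment: "Summary and Kaplan Meier curve by Response Category Based on Independent Reviewer-Assessed Response will be provided". Appendix 13 lists five outputs: Tables 2.10040 and 2.10041 (PFS), Table 2.10050 (OS), Figure 2.10010 (PFS) and Figure 2.10020 (OS). All are end-of-study deliverables, SAC [2]. The tables cite only the standard shell TTE1a. The figures carry only a reference to regqry_2020_10.

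**How response is established.** Section 7.1.1 limits the evidence: "Only the assessments from the start of treatment up to the earlier of confirmed disease progression or the start of new anti-cancer therapy" may be considered. In Table 3, row 11, a first response becomes NE if the next assessment is PD, or in this situation: "No subsequent disease assessment: subject died or discontinued study or started new anti-cancer therapy before further adequate disease assessment". Note 1 to Table 3 adds: "No minimal time interval is required for the subsequent disease assessment, but a different sample is required for confirmation".

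**The categories.** Section 7.2.2 lists the full set from sCR to NE, but for ORR and CBR. The split into PR or better against the rest is fixed only for a corneal summary (Section 8.2.3 item 7, repeated in the programming note to Table 3.0920). Figure 2.10080 applies the term 'Response Category' to duration of response, which exists only in responders.

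**The concern.** Response status is learned after the clock has started. To be counted as a confirmed responder, a patient must stay alive and progression-free, without new therapy, until a second adequate assessment. A patient who fails early is placed in another category because of that failure. The responder group thus has a stretch of follow-up in which, by construction, it can have no event, and the early events collect in the other groups. This is guarantee-time bias. Its direction is known wherever the grouping sets confirmed responders apart.

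At stake is interpretation. The gap between the curves mixes any real association with a gap made by the classification, and a reader cannot separate them. Such curves are easily taken to show that response prolongs PFS or OS.

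**Working it through.** **No figure to reproduce.** The SAP states no number for these displays. The check is how large a gap appears when response and outcome are unrelated.

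**Inputs from the SAP**
- Origin at randomization (7.2.1.5, 7.2.1.7).
- Disease assessment every 3 weeks (15.5.4).
- Confirmation on a later, different sample, with no minimum interval (Table 3, note 1).
- Design-alternative response rate 33% (3.1.1.1).

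**Assumptions (the SAP gives none of these)**
- Exponential event times with median PFS 3, 4 or 6 months and median OS 8, 12 or 16 months.
- Latent response in 20, 33, 45 or 60% of patients, independent of event time.
- Response at the first 3-weekly visit for everyone, or exponential with median 0.7, 1.4 or 2.8 months rounded up to the next visit.
- Confirmation 1 or 3 weeks later.
- Uniform censoring over 9-30 months (PFS) or 12-36 months (OS).
- Responder means confirmed before event and censoring. For OS only death blocks confirmation; since Table 3 also lets PD and new therapy block it, the OS model is conservative in that respect.
- Split: PR or better against the rest.

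**Closed-form case.** Everyone responds at week 3 and is confirmed at week 6, which is 42/30.44 = 1.38 months. With a true median PFS of 6 months, true 6-month PFS is 50%. Among confirmed responders it is 2^(-(6 - 1.38)/6) = 2^(-0.77) = 59%.

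**Simulation** (400,000 patients per scenario, no true association; rate = events per person-time; ranges over all scenarios)

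| Endpoint, median | Rate ratio, responders vs others | Event-free or alive: responders vs others (true in both) |
|---|---|---|
| PFS 3 months | 0.43-0.78 | 6 months: 31-53% vs 15-24% (25%) |
| PFS 4 months | 0.45-0.82 | 6 months: 41-63% vs 23-34% (35%) |
| PFS 6 months | 0.47-0.87 | 6 months: 55-75% vs 36-49% (50%) |
| OS 8 months | 0.51-0.90 | 12 months: 38-51% vs 25-35% (35%) |
| OS 12 months | 0.54-0.92 | 12 months: 53-65% vs 38-49% (50%) |
| OS 16 months | 0.55-0.92 | 12 months: 62-72% vs 47-59% (59%) |

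At 33% latent response the ratio is about 0.53-0.79 (PFS median 4 months) and 0.64-0.91 (OS median 12 months). The strongest values need 60% response and slow response together. The bias is smallest when few patients respond, all at the first visit, with quick confirmation.

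**After correction.** A landmark at week 6, 9 or 12 gives 0.97-1.02. Time-dependent response gives 0.99-1.01.

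**Related display.** Figure 1.00010 (time to treatment discontinuation by response category) is affected in the same direction but less. The response window in 7.1.1 does not close at the last dose, so response can still be confirmed after treatment stops.

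**The case against.** **The split is not in the SAP.** This stands. The full category list in 7.2.2 is at least as natural a source as a corneal table, and Figure 2.10080 uses the same term and the same regqry_2020_10 note where only responders exist. A reader might infer that PR or better against the rest is what the SAP plans. It is one reading among several. The full list would also set confirmed responders apart from other patients, so the direction carries over, but the sizes above were not computed for it. They do not apply to a split by depth among responders.

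**The method may be settled elsewhere.** This stands in part. regqry_2020_10 is not shown and may fix the categories or the method for the two figures. A reader might infer that a wrong analysis has been demonstrated. What is demonstrated is that the SAP text is silent and that the three tables do not cite that output.

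**Nothing depends on these displays.** This stands, and it sets the weight. Section 7.2.4 says that, unless otherwise specified, these endpoints "will be summarised using descriptive statistics, graphically presented (where appropriate) and listed". No test or decision rule uses response category for PFS or OS. A reader might infer that a biased hazard ratio is planned for them, but the Pike estimator belongs to duration of response (that bullet of 7.2.2, and Table 2.0062).

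**The sizes are assumed.** True. The range is wide, and the rate ratio is not a statistic that the SAP plans here. Only the direction is firm.

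**Conclusion.** The concern holds as a minor point. If the SAP text is followed as written, any grouping that sets confirmed responders apart, with the clock at randomization, favours responders even with no association. That follows from the SAP's own confirmation rules.

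The size is illustrative. It rests on assumed medians, response times and censoring, and on PR or better against the rest: about 0.43-0.87 for PFS and 0.51-0.92 for OS where the true ratio is 1. The OS effect may be modest.

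A reader might go further and infer that the efficacy conclusions are compromised. The SAP does not support that. The displays are descriptive and end-of-study only, and the primary ORR and the PFS and OS estimates by dose level do not use this grouping.

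**What to change.** In Section 7.2.2 and Appendix 13, define the response categories for Tables 2.10040, 2.10041 and 2.10050 and Figures 2.10010 and 2.10020. Then produce the five displays in one of two ways:

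- **Time-dependent response:** a patient moves to the responder group on the confirmation date, and nobody is excluded.
- **Pre-specified landmark** tied to the 3-weekly assessments: take patients still at risk, fix response status there, restart the clock there, and report the number excluded.

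If curves from randomization are kept, footnote that they do not show that response prolongs PFS or OS. If regqry_2020_10 already fixes the categories or method, state that in the SAP and apply it to the three tables as well. Put a corresponding footnote on Figure 1.00010.

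**Cost.** A few end-of-study displays need reprogramming. The time-dependent display is less familiar to read. A landmark loses early-event patients: the share lost is 1 - 2^(-t/median), with t the landmark in months. For median PFS of 3-4 months that is about 21-27% at week 6, 30-38% at week 9 and 38-47% at week 12. For median OS of 8-12 months it is about 8-11%, 11-16% and 15-21%. The footnote alone costs almost nothing but leaves the biased curves in the report.
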